## 8. Handling of Missing Data

Patients who died, were discharged, or dropped out were excluded. No imputation was used for missing values.

## 9. Analysis Population

Only patients who completed all six measurements were included in the analysis.

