STUDY DOCUMENT

Official Study Title:

The Effect of Prone Position on Oxygen Saturation, Blood Gas Parameters, and Respiratory Rate in Intensive Care Patients with COVID-19-induced ARDS

NCT Number: NCTXXXXXXX

Document Type: Study Protocol

Document Date: 26 May 2025

STUDY PROTOCOL

1. Official Title

The Effect of Prone Position on Oxygen Saturation, Blood Gas Parameters, and Respiratory Rate in Intensive Care Patients with COVID-19-induced ARDS

2. Brief Title

Effect of Prone Position in COVID-19 ARDS Patients

3. Principal Investigator(s)

- [name], RN, Ph.D. – Diyarbakır Provincial Health Directorate
- [name]. [name], Ph.D. – Inonu University Faculty of Nursing

4. Study Sites

General and Intermediate Intensive Care Units, Eastern Turkey

5. Study Period

Start Date: April 1, 2021

End Date: August 30, 2021

6. Background and Rationale

ARDS is a common complication of severe COVID-19, associated with high mortality. Prone positioning has been shown to improve oxygenation and lung compliance in ARDS. This study investigates its short-term effectiveness in non-intubated patients.

7. Objectives

To evaluate the impact of a 30-minute prone position on:

- Oxygen saturation (SpO₂, SaO₂, PO₂)
- Respiratory rate
- Blood gas parameters (pH, PCO₂, Lactate, Sodium)

8. Study Design

Randomized controlled trial

Parallel group, repeated measures (6 total timepoints)

1:1 allocation (n = 90, 45 per group)

9. Eligibility Criteria

Inclusion Criteria:

- Age ≥ 40
- ICU hospitalization for COVID-19-induced ARDS
- Intubated and responsive to assessment

Exclusion Criteria:

- Sensory impairments (vision/hearing)

- Cognitive impairments
- Patients who died or no longer required ICU during study

10. Intervention

Experimental Group: 30 minutes prone position once daily for 2 days

Control Group: Supine standard care

11. Outcomes

Primary Outcome:

- Change in oxygen saturation (SpO_2) post-prone positioning

Secondary Outcomes:

- Respiratory rate
- Arterial blood gas values (SaO_2 , PO_2 , PCO_2 , pH, lactate, sodium)

12. Randomization

Simple randomization by drawing lots

Allocation ratio 1:1

13. Blinding

Open-label (no blinding)

14. Statistical Methods

Paired and independent t-tests

Wilk's Lambda

Cohen's d for effect size

SPSS used for data analysis

15. Ethical Considerations

Approval: Gazi Yasargil Training and Research Hospital Ethics Committee (15.01.2021 / No: 626)

Verbal and written consent obtained

Conducted per Declaration of Helsinki

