## 4. Sample Size Justification

A total of 90 patients (45 per group) were selected using 95% confidence level, 5% margin of error, and an effect size of 0.70.

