## 5. Randomization

Random assignment was done by drawing lots from every four eligible ICU admissions each day.

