## 7. Statistical Methods

- Descriptive statistics: mean, standard deviation, frequency, and percentage
- Inferential statistics: Wilk's Lambda for repeated measures, paired t-tests, independent t-tests
- Effect size: Cohen's d
- Software: SPSS v22

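### The only stated primary analysis keeps six-reading completers and drops deaths, discharges and drop-outs, so any loss after allocation takes the SpO2 comparison outside the protection of randomisation

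*SAP*

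**What the plan says.** Three statements together define who is analysed:

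- SAP 9 (Analysis Population): "Only patients who completed all six measurements were included in the analysis".
- SAP 8 (Handling of Missing Data): "Patients who died, were discharged, or dropped out were excluded. No imputation was used for missing values".
- Protocol 9 (Eligibility Criteria) lists as an exclusion: "Patients who died or no longer required ICU during study". This describes something that happens in the course of the study, not a baseline characteristic.

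SAP 7 gives the tests: "Inferential statistics: Wilk's Lambda for repeated measures, paired t-tests, independent t-tests". In its multivariate repeated-measures form, Wilk's Lambda needs every reading. The t-tests need only the readings they compare, so for them the restriction comes from SAP 9 alone.

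On numbers, Protocol 8 attaches 90 patients, 45 per group, to the allocation, while SAP 4 says "A total of 90 patients (45 per group) were selected". Neither says how many of those allocated completed, or whether excluded patients were replaced. On timing, SAP 5 says "Random assignment was done by drawing lots from every four eligible ICU admissions each day", so some exclusions may precede the draw. Protocol 13 makes the trial open-label.

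**The concern.** Randomisation balances the arms at allocation. It protects the comparison only if membership of the analysis set does not depend on what happens afterwards. Here membership depends on survival, on still being in the ICU, on not dropping out and on having all six readings. Each is plausibly related to oxygenation, and staff and patients know the arm.

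The direction cannot be predicted. Losing more worsening prone patients favours prone. Losing more worsening controls, or losing improving prone patients through discharge, works against it. Equal losses do not settle the matter, because deaths and discharges remove opposite kinds of patient.

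Exclusions made before the draw do no harm. But completion of six readings cannot generally be known before allocation, so SAP 9 acts at least partly after it. Without loss counts by arm, a reader can judge neither the size nor the direction of any bias in the primary outcome.

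**Working it through.** **Inputs from the documents.** 45 per arm (Protocol 8, SAP 4); effect size 0.70 and 95% confidence (SAP 4); two days of treatment (Protocol 10). No loss counts, power or dropout allowance are given. Every loss count and correlation below is an assumption.

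**1. The plan's own figure.** Without a stated power or sidedness, 90 cannot be uniquely reproduced. Reading 0.70 as a two-group standardised difference at two-sided alpha 0.05, the exact t calculation needs 44 per arm for 90% power. With noncentrality 0.70/√(1/n₁ + 1/n₂):

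| Analysed | Noncentrality | Power |
|---|---|---|
| 45 v 45 | 3.320 | 90.7% |
| 42 v 44 | 3.245 | 89.4% |
| 36 v 45 | 3.130 | 87.1% |

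Lost power is therefore secondary. These figures apply only if 45 per arm were allocated, not if 90 is a completer count after replacement.

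**2. Bias in the change score, no true effect.** Give each patient a prognosis score correlated r_B with baseline SpO2 and r_F with follow-up SpO2. If the k patients with the worst scores of 45 are lost, the mean score of the rest rises by m(k) = S(k)/(45 − k), where S(k) is the expected sum of the k most extreme of 45 standard normal values, in absolute terms:

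| k | 1 | 2 | 3 | 4 | 6 | 9 |
|---|---|---|---|---|---|---|
| m(k) | 0.050 | 0.093 | 0.133 | 0.171 | 0.242 | 0.342 |

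Bias, prone minus control, in SD of one reading = (r_F − r_B) × [m(k prone) − m(k control)].

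- r_B = r_F = 0.5: the first factor is zero, so bias is 0.00 for every split and false positives stay at about 5%.
- r_B = 0.5, r_F = 0.7: 4 v 0 gives 0.2 × 0.171 = +0.03; 9 v 0 gives 0.2 × 0.342 = +0.07.
- r_B = 0.3, r_F = 0.7: the results are below. False-positive rates come from simulated t-tests on change, 20,000 trials each, with baseline–follow-up correlation 0.6 and 0.8.

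| Lost, prone v control | Calculation | Bias | False positives |
|---|---|---|---|
| 1 v 0 | 0.4 × 0.050 | +0.02 | 5–6% |
| 3 v 1 | 0.4 × (0.133 − 0.050) | +0.03 | about 6% |
| 4 v 0 | 0.4 × 0.171 | +0.07 | 7–9% |
| 6 v 0 | 0.4 × 0.242 | +0.10 | 8–12% |
| 9 v 2 | 0.4 × (0.342 − 0.093) | +0.10 | 8–13% |
| 9 v 0 | 0.4 × 0.342 | +0.14 | 11–18% |

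Swapping the arms reverses the sign (0 v 4 gives −0.07). Equal losses of the same kind give 0.00. Equal losses of opposite kinds (sickest prone, best control) add: 4 v 4 gives 0.4 × 2 × 0.171 = +0.14, with 12–19% false positives. If loss is probabilistic (log-odds 1.5 per SD) instead of strictly the sickest, 4 v 0 gives +0.05 and 9 v 0 gives +0.10.

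**3. All six readings, and the alternative analysis.** Simulation with AR(1) correlation 0.8 or 0.9 per step and monotone loss compared completers' change (reading 6 minus reading 1) with a baseline-adjusted, unstructured-covariance likelihood estimate from all available readings. Low loss means 7% v 2% or 9% v 0%; high loss means 20% v 5% or 20% v 0%. Bias is in SD of one reading.

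| Loss depends on | Loss | Completers | Mixed model |
|---|---|---|---|
| an observed fall | low | +0.02 to +0.14 | 0.00 |
| an observed fall | high | +0.07 to +0.26 | 0.00 |
| an unseen fall | low | +0.03 to +0.16 | +0.01 to +0.05 |
| an unseen fall | high | +0.08 to +0.31 | +0.03 to +0.11 |
| an unseen level only | low | 0.00 to +0.02 | +0.01 to +0.03 |
| an unseen level only | high | +0.02 to +0.03 | +0.04 to +0.07 |

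When loss follows a fall, the completers' Wilk's Lambda arm-by-time test rejects in 5–7% of null trials at low loss and 6–14% at high loss.

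**The case against.** The best counter-argument is that no harm is shown. The documents report no losses, treatment lasts two days, and at 1 v 0 to 4 v 0 lost the bias in the change-score model is at most 0.07 SD. Double-digit false-positive rates need heavy one-sided loss or losses of opposite kinds. That stands, and it limits what can be said about size. It does not remove the rule, and the missing counts are the reason the size is unknown.

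The interval of change is also undefined: SAP 6 speaks of six time points and Protocol 11 of change after proning, and neither names a baseline. If change is taken across one 30-minute session, prognosis may correlate similarly with both readings, and the equal-correlation case gives zero bias. That stands as one end of the range.

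Replacement of excluded patients would change the loss fractions and make the power figures inapplicable. The documents are silent on it; numbers randomised and analysed per arm would show it.

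Finally, the mixed model is not uniformly better. When loss depends on an unseen level, which is plausible for deaths, it has about twice the completers' bias. It also treats SpO2 after death as a value that could have been measured. Both points stand, so it should not be adopted without the sensitivity analyses below.

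**Conclusion.** The concern holds as a statement about the rule. The sole stated analysis of the primary outcome conditions on events that can follow allocation, and nothing elsewhere in either document offsets this. Confidence in that reading is high. Material bias is not demonstrated.

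Under assumed losses with 45 allocated per arm, the bias in a single change score runs from zero (complete follow-up, or loss equally related to baseline and follow-up) through about 0.07 SD at 4 v 0 to about 0.14 SD at 9 v 0 or at 4 v 4 of opposite kinds. In the six-reading model it reaches 0.31 SD when 20% of one arm is lost after an unseen fall. The sign depends on which arm loses which patients. The point needs correcting before the result is presented as a randomised comparison; if the records show no loss after allocation, one sentence saying so resolves it.

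**What to change.** **Minimum, whatever records exist.**

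- SAP 8: replace the exclusion with a table of deaths, discharges and drop-outs by arm, with reason and last reading obtained.
- SAP 9: report numbers randomised and analysed per arm, and label the present result completers-only.
- Protocol 9: if the line on death or leaving the ICU was applied after allocation, say so and state that it is not an eligibility criterion.

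This costs a table and some wording, with no reanalysis.

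**Where partial readings exist.**

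- SAP 9: make the primary set all randomised patients, as allocated.
- SAP 6: name the baseline reading.
- SAP 7: make the primary analysis a mixed model for repeated measures on every available SpO2 value, with arm, time, arm-by-time and baseline SpO2. Keep the completers' Wilk's Lambda and t-tests as sensitivity analyses.
- Add one sensitivity analysis ranking deaths worst, and one shifting unobserved SpO2 over a stated range by arm, separately for discharges and drop-outs.

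This part needs a reanalysis and surviving partial records. The study ended in August 2021 and the documents do not say such records were kept, so it may be impossible. The mixed model assumes data are missing at random, which is why the two added sensitivity analyses are part of the change.

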## **10. Version History**

Version 1.0

Date Last Updated/Approved: 26 May 2025
